## 15.2 Laboratory parameters, vital signs, and ECG parameters

This section defines the general principles for the analysis of categorical and continuous parameters, unless specified otherwise. In general, the analysis of all parameters will be done by visit and, if applicable, by time point.

Categorical parameters will be descriptively summarized by presenting the number and percentage of subjects per visit/time point, and overall post-baseline. For an overall post-baseline analysis, the worst value during the on-treatment period, including unscheduled visits, will be derived.

Continuous parameters will be descriptively summarized. Change from baseline will be presented for all post-baseline visits/time points. Baseline values are defined as described in Section 8.2.2. If reference ranges for a parameter differ between subject groups, e.g., based on sex or age group, the analysis of the parameter will be presented separately for each subject group.

Continuous parameters will be classified as *low*, *normal*, or *high* based on reference ranges, and for parameters where sponsor alert ranges are defined, parameters will be classified as *alert low*, *non-alert*, or *alert high* based on sponsor-defined alert ranges. For an overall post-baseline analysis, the values out of range during the on-treatment period, including unscheduled visits, will be summarized per subject. If a subject has parameter values flagged as *low* and values flagged as *high*, the parameter will be classified as *low+high*.

A summary of the number and the percentage of subjects with values flagged as *alert low*, *non-alert*, *alert high* with respect to alert ranges will be provided for each continuous parameter where sponsor alert ranges are defined at each visit/time point and overall post-baseline.

Shift tables from baseline for the different visits /time points and overall post-baseline will be generated for each continuous parameter flagged as *low*, *normal*, or *high* with respect to reference ranges. Percentages will be calculated for each baseline category (*low*, *normal*, or *high*) using the number of subjects in the corresponding post-baseline categories.

Graphical presentations of the time course of continuous parameters and corresponding changes from baseline will be provided (mean and 95% confidence interval). At each visit/time point, the plots will show the total number of subjects. On the bottom the number of subjects flagged as *low*, and on the top the number of subjects flagged as *high* based on reference ranges, and *alert low* or *alert high* based on sponsor-defined alert ranges will be shown by treatment.

Shift plots by visit/time point will be provided for the continuous parameters with reference ranges and sponsor-defined alert ranges marked by vertical and horizontal lines.

A listing of subjects with values outside the sponsor-defined alert ranges will be provided.

All parameter values will be presented in a subject data listing. For continuous parameters, values out of reference ranges will be flagged as H (high) or L (low) in the listing. If a value classified as high or low is in addition also out of sponsor-defined alert ranges, it will be flagged as H\* or L\* in the listing.

Unscheduled measurements of parameters will be presented in the subject data listing. In general, unscheduled measurements will not be included in the analysis. However, they will be taken into account in the calculation of the overall post-baseline classification of parameters.

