### 9.3.2 Subject discontinuation from the IMP

Discontinuation of IMP applies only to the treatment period. Subjects who are discontinued from IMP should not be discontinued from the trial except for the reasons indicated in [Table 1](#). Subjects who are discontinued from IMP should be encouraged to remain in the trial for their own safety and for the integrity of the trial.

Subjects must be evaluated prior to each infusion of IMP. The investigator must permanently or temporarily discontinue treatment with IMP for any reasons listed in [Table 2](#). The investigator may decide to temporarily discontinue a subject from receiving IMP for other reasons if further assessments may be helpful to assure safety of the subject. The investigator may also choose to permanently discontinue a subject from treatment if they believe that continued exposure of the subject to neridronic acid may pose an undue risk to the subject, e.g., due to particular adverse events or due to deterioration in the subject's health for reasons related or unrelated to the treatment.

In situations where treatment is temporarily discontinued, the treatment period may be extended to a maximum of 21 days (i.e., Visit 5 should occur no later than 21 days after Visit 2). Visit 6 will be scheduled to occur 4 days ( $\pm 2$  days) after Visit 5, but all subsequent visits should occur as originally scheduled relative to Visit 2 (e.g., Visit 7 will be 42 days [6 weeks] after Visit 2). No more than 4 infusions may be administered during the treatment period, and a minimum of 48 hours between any 2 infusions is required.

Table 2: Reasons for permanent and temporary discontinuation of subjects from IMP

Reason	Discontinuation from IMP	
	Permanent	Temporary
Symptomatic hypocalcemia.	X	
Serum calcium <7.8 mg/dL (<1.95 mmol/L). The subject may resume treatment following investigator assessment and a repeat serum calcium value above this limit (albumin-corrected serum calcium should be considered if serum albumin is below 3.5 g/dL).		X
Clinical signs of dehydration (e.g., dizziness, palpitations, confusion).		X
Evidence suggestive of a possible change in renal function:		

 
A persistent <math>\geq 25\%</math> decrease from baseline (last value observed prior to treatment) in the eGFR, based on repeated central laboratory results from blood samples obtained at least 1 week apart a.
 
	X	

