
 
A <math>\geq 25\%</math> decrease from baseline in the eGFR. If a repeated measurement of eGFR is within 75% or more of the baseline value, the subject may resume treatment a.
 
		X

 
A persistent urinary ACR >300 mg/g based on quantitative urinary albumin and creatinine data from the central laboratory, with urine samples obtained at least 1 week apart.
 
	X	

 
A urinary ACR >300 mg/g based on the results of the semi-quantitative dipstick or quantitative data from the central laboratory. The subject may resume treatment if quantitative urinary albumin and creatinine data from the central laboratory indicate a urinary ACR value <150 mg/g.
 
		X

 
A persistent eGFR <50 mL/min/1.73 m^2 and urinary ACR >150 mg/g based on repeated quantitative data from the central laboratory, with blood and urine samples obtained at least 1 week apart.
 
	X	
An average QTcF interval of >500 ms based on triplicate ECGs, or average QTcF interval of >480 ms with a concurrent increase in average QTcF interval >60 ms relative to the average of triplicate ECGs obtained at Visit 1.	X	
Pregnancy.	X	
Development of hypersensitivity to the IMP.	X	
Signs or symptoms of ocular inflammation: b		

 
Resolution of signs and symptoms within 5 days.
 
		X

 
Persistent or recurrent signs and symptoms.
 
	X	

Reason	Discontinuation from IMP	
	Permanent	Temporary
At any point during the treatment period if further assessment may be helpful to assure safety of the subject.		X
Any other adverse event causing a significant deterioration in subject's health.		X
Major protocol deviations (e.g., serious non-compliance with protocol procedures, unsafe use of prohibited medication, abuse of illicit drugs, or other reckless behavior during the trial that may jeopardize the subject's safety or safety of other subjects or site staff).	X	

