### **12.3.5 Safety laboratory**

Laboratory tests (except for urine dipsticks for urine drugs of abuse testing and urine pregnancy testing) will be performed by a central safety laboratory. At Visit 2, Visit 3, Visit 4, and Visit 5, in addition to taking blood and urine samples for evaluation at the central safety laboratory, an assessment of urinary ACR will be performed prior to infusion using a semi-quantitative dipstick.

The use of any clinical laboratory facility other than the designated central safety laboratory is not allowed. The only exception is in the case of an emergency where the investigator requires the results quickly.

A table of the reference ranges for each of the laboratory parameters measured with a description of the methods will be provided by the central safety laboratory before the trial start and is to be filed in the investigators site file.

Changes in the reference ranges or in the methodology during the course of the trial are to be communicated by the central safety laboratory to the sponsor who will inform the investigators.

Alert ranges for specific laboratory parameters will be provided by the sponsor to the central safety laboratory. Any laboratory value within these alert ranges will be immediately reported to the investigator.

The sites will be provided with a manual by the central laboratory specifying the specimen collection, preparation, packaging, and transport of all clinical laboratory tests required by this protocol.

Throughout the clinical part of the trial, the investigator must provide a comment in the CRF regarding the clinical relevance of any laboratory values outside of the sponsor-defined alert range. Any abnormal laboratory result considered clinically relevant will be followed until it reaches a satisfactory resolution, becomes stable, or can be explained by other causes (e.g., concurrent condition or medication), and clinical judgment indicates that further evaluation is not needed. The printout of the laboratory values will be stored with the source data.

Data will be transferred from the central safety laboratory to the sponsor electronically.

The following tests will be performed:

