### **15.2.1 Laboratory parameters**

Central laboratory parameters will be analyzed as described in the following paragraphs. Local laboratory assessments, pregnancy tests, and drugs of abuse tests will only be listed.

In general, all central laboratory parameters will be reported using Système International d'Unités (SI) units. Selected parameters will additionally be reported using US conventional units to facilitate safety data review. The corresponding analyses of these parameters will be repeated using values in US conventional units. The list of parameters will be provided in a separate spreadsheet attached to the data management plan.

Continuous and categorical laboratory parameters will be analyzed as described in Section 15.2 with individual specifications outlined in Table 3. The analysis of continuous laboratory parameters will be done by parameter group (clinical chemistry, clotting, hematology, and urinalysis). Categorical urinalysis parameters will be additionally classified as *normal* or *abnormal*.

Graphical presentations of the mean time course of the continuous parameters alkaline phosphatase, calcium (measured), creatinine (serum), estimated glomerular filtration rate (eGFR), and calculated urinary albumin/creatinine will be provided (mean and 95% CI). The graph covers the 12-month trial period presenting the means from Visit 1 through Visit 11. Similarly, a graphical presentation of the mean time course of the change from baseline of the 5 parameters will be provided. The mean time course of each parameter and the corresponding change from baseline will be presented in 1 plot. The plots will be presented in US conventional units.

Shift plots by visit will be provided for the same parameters. The plots will be presented in US conventional units.

A graphical presentation of the mean time course of the laboratory parameters serum calcium (measured), urinary calcium and parathyroid hormone, and the bone turnover marker BAP (Section 14.2.1) will be created (mean and 95% CI). The 4 mean plots will be presented as a single panel plot on the same page. The plot will be presented in US conventional units.

Subjects potentially qualifying for Hy's law criteria (FDA 2009), i.e., subjects showing post-baseline abnormal hepatic values, will be presented in a separate listing. Subjects fulfilling the following 2 criteria potentially qualify for Hy's law:

- ALT >3x ULN or AST >3x ULN.
- Total bilirubin >2x ULN.

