**20.3 Reference ranges and alert ranges**

Vital signs and ECG parameters will be flagged as low or high based on reference ranges and sponsor-defined alert ranges, respectively. This section defines the reference and alert ranges for vital signs, and the alert ranges for ECG parameters.

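### The SAP classifies laboratory and ECG values only against absolute ranges, so no table counts subjects whose eGFR falls by at least 25%, the protocol's own renal signal

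*SAP*

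**What the plan says.** **Protocol, Section 9.3.2, Table 2.** IMP is stopped permanently for a persistent fall of 25% or more, worded as "decrease from baseline (last value observed prior to treatment) in the eGFR, based on repeated central laboratory results", with samples at least 1 week apart. A single fall of that size is a temporary hold, and treatment may resume if the repeat is back to 75% or more of baseline. Footnote a ties the check to the Visit 3 and Visit 4 samples, and the section limits IMP discontinuation to the treatment period. Further renal criteria use ACR >300 mg/g, and eGFR <50 together with ACR >150 mg/g. The QT criterion is an average QTcF >500 ms, or >480 ms "with a concurrent increase in average QTcF interval >60 ms relative to the average of triplicate ECGs obtained at Visit 1".

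**SAP 15.2, 15.2.1 and 15.2.3.** Values are classed by reference range and, where one exists, by alert range: "based on reference ranges, and for parameters where sponsor alert ranges are defined, parameters will be classified as". Subjects in each alert class are counted by visit and overall post-baseline. Change is handled as a continuous variable: "Change from baseline will be presented for all post-baseline visits/time points". eGFR and ACR also get mean plots and shift plots.

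**Ranges.** On SAP 20.3: "This section defines the reference and alert ranges for vital signs, and the alert ranges for ECG parameters". Table 9 there sets the QTcF alert-high limit at >480 ms. Neither document prints a reference or alert limit for eGFR or ACR. Protocol 12.3.5 says the sponsor supplies laboratory alert ranges separately.

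**Related counts.** SAP 10.1 has a row for subjects who discontinued IMP because renal function deteriorated. Protocol 12.3 requires abnormal values that the investigator judges clinically relevant to be recorded as adverse events.

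**The concern.** Protocol 8.2 treats renal toxicity as a class risk of intravenous bisphosphonates and answers it with defined stopping criteria. A reader of the report will want to know how many of about 290 subjects met those criteria over the year of follow-up. An absolute-range table cannot answer that for a relative criterion. It could truthfully show few or no shifts in eGFR while several subjects had lost a quarter of their filtration rate.

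Timing adds to this. Under protocol 11.2, treatment-period procedures come before the infusion unless stated otherwise. Visit 5 blood is therefore drawn before the fourth infusion by default, and the first scheduled sample after the full 400 mg is Visit 6. By then the stopping rule no longer applies, so a fall cannot reach the SAP 10.1 row.

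**Working it through.** The plan gives no figure of its own on this point to reproduce. The sample size of about 290 carries no rate or precision target.

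**1. eGFR fall against an absolute limit.** Inputs: entry requires eGFR of at least 60 mL/min/1.73 m² (exclusion criterion 1), and the signal is a fall of at least 25%. The lower reference limit L is not given, so three values are assumed. A fall of exactly 25% lands on L when baseline = L / 0.75.

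| Assumed L | L / 0.75 | Baselines at which a 25% fall changes no category |
|---|---|---|
| 60 | 80 | 80 or more (normal to normal) |
| 75 | 100 | 60 to below 75 (low to low), or 100 or more |
| 90 | 120 | 60 to below 90 (low to low), or 120 or more |

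Larger falls can also be hidden: with L = 60, a 40% fall from 100 gives 60, still normal.

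The share of subjects affected depends on a baseline distribution that the documents do not give. If it is assumed normal, with mean/SD between 90/16 and 100/15 and truncated at 60, the share is 76% to 91% for L = 60 and 34% to 52% for L = 90.

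**2. What the continuous summaries show.** Suppose 5 of 290 subjects each lose 30 mL/min. The mean moves by 5 × 30 / 290 = 0.5 mL/min. The first quartile needs about 290 / 4 = 73 subjects to move it. The minimum change would show the single worst value, but in absolute units: a loss of 24 is 24/80 = 30% from a baseline of 80 (signal met) and 24/120 = 20% from 120 (not met).

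**3. Which samples feed the stopping rule.** Scheduled post-baseline laboratory visits are Visits 3 to 11, that is 9. The rule uses 2 of them (Visits 3 and 4), which leaves 7 (Visits 5 to 11).

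**4. Spacing of repeats.** Visits 3 and 4 are nominally 7 − 4 = 3 days apart, and Visits 3 and 5 are 10 − 4 = 6 days apart. Consecutive scheduled values in the treatment period therefore do not meet the 1-week condition, and a persistence count has to use actual dates.

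**5. QTcF rule against the alert range.** Both arms of the protocol rule require QTcF >480 ms, so everyone who meets it is alert high. On a 1-ms grid (baseline 300 to 470, post-dose 300 to 599), no point met the rule without also being alert high. The reverse fails: 810 grid points were alert high without meeting the rule. For example, 470 to 500 ms is alert high with a rise of only 30 ms.

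**6. Would a count be informative at N = 290?** At an assumed true rate of 1%, the chance of at least one case is 1 − 0.99^290 = 94.6%. With 0 of 290, the two-sided exact 95% upper bound is 1 − 0.025^(1/290) = 1.26%.

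**The case against.** The best defence is that Table 2 contains treatment-stopping rules, not endpoints. Protocol 14.1.6.2 promises descriptive summaries plus summaries of alert-range and abnormal values, and the SAP delivers those. This stands: the SAP does not breach the protocol.

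Nor is the information lost. Change from baseline is reported with minimum and quartiles, eGFR has shift plots by visit, and every value is listed. That stands too, but a reader would have to add a 25% line to the plot or work through listings to obtain a number. The adverse event tables, including the action-taken category for interrupted drug, may pick up some cases, but only where the investigator judged the value clinically relevant.

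The laboratory alert ranges are also outside the documents. They may already count ACR >300 mg/g. They cannot count a relative eGFR fall, because an absolute limit cannot express one.

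Three stronger readings are tempting, and the documents do not support them.
- *That subjects meeting Table 2's signals are counted nowhere.* Those meeting the QT rule are all within the counted alert-high group, and permanent renal discontinuations have their own row.
- *That a QTcF rise above 60 ms is itself a protocol signal.* It applies only together with QTcF >480 ms.
- *That the most extreme values are lost because emergency local results are left out.* The SAP says "Local laboratory assessments, pregnancy tests, and drugs of abuse tests will only be listed", and the protocol says of non-central laboratories "The only exception is in the case of an emergency where the investigator requires the results quickly". But SAP 15.2.1 uses the term local laboratory assessment for the routine ACR dipstick at the four infusion visits. The documents do not say whether emergency results reach the CRF. The eGFR rule and the persistent ACR rule rest on central results, so local values do not explain the missing eGFR count.

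**Conclusion.** The point holds for eGFR. No planned table gives the number of subjects with a fall of at least 25%, single or persistent. Resolved holds, and falls first seen at 7 of the 9 scheduled post-baseline laboratory visits, are outside both the stopping rule's reach and the discontinuation row.

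How much the shift tables hide depends on an unstated reference limit and an unknown baseline distribution, so no single percentage should be quoted. What needs only an assumed limit is the baseline range: 80 and above for a limit of 60; below 90 or 120 and above for a limit of 90.

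For QTcF the defect is smaller: subjects meeting the rule are counted but cannot be told apart from others above 480 ms.

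The primary endpoint is not affected. This is a cheap improvement to the safety reporting.

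**What to change.** In SAP 15.2.1 and 15.2.3, add the number and percentage of Safety Set subjects, by visit and overall post-baseline including unscheduled central values, with:

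- (a) an eGFR decrease of at least 25% from the Visit 2 pre-dose value, shown as single and as persistent, where persistent means samples at least 1 week apart by actual date, as in Table 2;
- (b) central-laboratory ACR >300 mg/g, and eGFR <50 with ACR >150 mg/g, where the alert ranges do not already count them;
- (c) QTcF >500 ms, and QTcF >480 ms with a rise >60 ms relative to the Visit 1 triplicate mean.

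State the reference point in (c) explicitly. Table 2 uses Visit 1 for the QTcF rise, while the SAP baseline is generally Visit 2.

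The cost is a few extra tables from data already collected. The reported safety figures may look slightly less favourable. Nothing in the conduct of the trial or in Table 2 itself needs to change.

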### **15.2.1 Laboratory parameters**

Central laboratory parameters will be analyzed as described in the following paragraphs. Local laboratory assessments, pregnancy tests, and drugs of abuse tests will only be listed.

In general, all central laboratory parameters will be reported using Système International d'Unités (SI) units. Selected parameters will additionally be reported using US conventional units to facilitate safety data review. The corresponding analyses of these parameters will be repeated using values in US conventional units. The list of parameters will be provided in a separate spreadsheet attached to the data management plan.

Continuous and categorical laboratory parameters will be analyzed as described in Section 15.2 with individual specifications outlined in Table 3. The analysis of continuous laboratory parameters will be done by parameter group (clinical chemistry, clotting, hematology, and urinalysis). Categorical urinalysis parameters will be additionally classified as *normal* or *abnormal*.

Graphical presentations of the mean time course of the continuous parameters alkaline phosphatase, calcium (measured), creatinine (serum), estimated glomerular filtration rate (eGFR), and calculated urinary albumin/creatinine will be provided (mean and 95% CI). The graph covers the 12-month trial period presenting the means from Visit 1 through Visit 11. Similarly, a graphical presentation of the mean time course of the change from baseline of the 5 parameters will be provided. The mean time course of each parameter and the corresponding change from baseline will be presented in 1 plot. The plots will be presented in US conventional units.

Shift plots by visit will be provided for the same parameters. The plots will be presented in US conventional units.

A graphical presentation of the mean time course of the laboratory parameters serum calcium (measured), urinary calcium and parathyroid hormone, and the bone turnover marker BAP (Section 14.2.1) will be created (mean and 95% CI). The 4 mean plots will be presented as a single panel plot on the same page. The plot will be presented in US conventional units.

Subjects potentially qualifying for Hy's law criteria (FDA 2009), i.e., subjects showing post-baseline abnormal hepatic values, will be presented in a separate listing. Subjects fulfilling the following 2 criteria potentially qualify for Hy's law:

- ALT >3x ULN or AST >3x ULN.
- Total bilirubin >2x ULN.

Table 3: Analysis of laboratory parameters

Parameter group	Parameter	Table of descriptive statistics	Frequency table (low/high)	Shift table	Mean plot	Shift plot
Clinical chemistry parameters (continuous)	Albumin	X	X	X		
	Alkaline phosphatase	X	X	X	X	X
	ALT	X	X	X		
	AST	X	X	X		
	Bicarbonate	X	X	X		
	BUN	X	X	X		
	Calcium (measured)	X	X	X	X	X
	Calcium (albumin-corrected)	X	X	X		
	Chloride	X	X	X		
	Cholesterol	X	X	X		
	Creatine phosphokinase	X	X	X		
	Creatinine (serum)	X	X	X	X	X
	eGFR	X	X	X	X	X
	GGT	X	X	X		
	Glucose	X	X	X		
	LDH	X	X	X		
	Lipase	X	X	X		
	Magnesium	X	X	X		
	Parathyroid hormone	X	X	X	X	X
	Phosphorus	X	X	X		
	Potassium	X	X	X		
	Sodium	X	X	X		
	Total bilirubin	X	X	X		
Total protein	X	X	X			
Triglycerides	X	X	X			
Uric acid	X	X	X			
Vitamin D	X	X	X	X	X	
Hematology parameters (continuous)	Hematocrit	X	X	X		
	Hemoglobin	X	X	X		
	MCH	X	X	X		
	MCHC	X	X	X		

Parameter group	Parameter	Table of descriptive statistics	Frequency table (low/high)	Shift table	Mean plot	Shift plot
	MCV	X	X	X		
	Platelet count	X	X	X		
	RBC count	X	X	X		
	WBC count a	X	X	X		
Urinalysis parameters (continuous)	Albumin (microalbumin)	X	X	X		
	Calcium	X	X	X	X	X
	Creatinine	X	X	X		
	Calculated urinary albumin/creatinine ratio	X	X	X	X	X
	pH b	X	X	X		
Urinalysis parameters (categorical)	Bilirubin b	X		X		
	Blood (erythrocytes) b	X		X		
	Glucose b	X		X		
	Ketone b	X		X		
	Leukocyte esterase b	X		X		
	Nitrite b	X		X		
	Protein b	X		X		
	Urobilinogen b	X		X		

a) With differential count if abnormal: includes neutrophils, lymphocytes, monocytes, basophils, eosinophils (absolute count and percent).

b) Dipstick assessment.

ALT = alanine aminotransferase; AST = aspartate aminotransferase; BUN = blood urea nitrogen; eGFR = estimated glomerular filtration rate; GGT = gamma-glutamyl transferase; LDH = lactic acid dehydrogenase; MCH = mean corpuscular hemoglobin; MCHC = mean cell hemoglobin concentration; MCV = mean cell volume; RBC = red blood cell; WBC = white blood cell.

On Day 1, Day 4, Day 7, and Day 10, additional urine samples will be obtained prior to infusion for local laboratory assessment of urinary albumin creatinine ratio (ACR) at the site using a semi-quantitative dipstick. The results will be presented in a subject data listing.

If a dipstick test is positive (except for glucose or ketones, and blood/leucocytes in menstruating subjects), a microscopic examination of urine sediment will be performed to determine the presence of red blood cells, white blood cells, epithelial cells, crystals, casts, and bacteria. The results will be presented in a subject data listing.

Urine samples will be obtained from women of child-bearing potential (Visit 1 through Visit 5, Visit 9, and Visit 11) and tested locally using a urine  $\beta$ -human chorionic gonadotropin ( $\beta$ -HCG) pregnancy dipstick test. The results will be presented in a subject data listing.

Urine samples will be obtained from all subjects at the Enrollment Visit for testing for drugs of abuse. The drugs to be screened for using suitable validated methods (e.g., dipstick) include: cocaine, 3,4-methylenedioxy methamphetamine, ecstasy (MDMA), amphetamines, cannabinoids. The results will be presented in a subject data listing.

